BACKGROUND/ RATIONALE	Zilretta is approved for intra-articular injection into the knee joint for treatment of osteoarthritis (1). There are ongoing studies for intra-articular injection into the other large joints including the shoulder and hip joints (2). To our knowledge, there has been no prior study to prove efficacy of injection of the extended release steroid into the bursa. The bursae surrounding the hip joint including the iliopsoas and the greater trochanteric bursa are some of the larger bursae in the body. Conventional treatment for inflammation of these bursae is injection of corticosteroids (3). We believe that a long acting corticosteroid, if efficacious, can have a great impact. There is a significant population of patients suffering from chronic bursal pain, who might benefit. At our institute, bursal injection of the steroid in the region of hips is one of the most common locations, second to joint injections. To our understanding, the bursa surrounding the hip are deep enough to avoid side effects associated with subcutaneous injection of steroid. The current proposal is a pilot study.
STUDY DESIGN	This is a prospective, open-label, pilot study, to assess the safety and efficacy of FX006 (triamcinolone acetonide extended release injectable suspension 32 mg) , administered to patients with greater trochanteric bursitis.
PRIMARY OBJECTIVE	The primary objective will be to determine the safety and efficacy of this drug in bursal injections by monitoring the improvement in the pain from baseline, as established using the using a Numeric Pain Rating Scale (NPRS) score at the end of 12 weeks.
SECONDARY OBJECTIVES	Secondary objective is to determine any alteration in the Patient Global Impression of Change (PGIC) measure. This is used as an indicator to assess the patient's impression to change in treatments, to their chronic pain.
PRIMARY END POINT	The primary endpoint will be the improvement in the pain from baseline, at the end of week 12, as determined by the NPRS pain score
SECONDARY END POINT	The secondary endpoint will be any alteration in the PGIC measure, at the end of week 12.

NUMBER OF SUBJECTS

24 patients

SUBJECT SELECTION CRITERIA	
Inclusion Criteria:
 
• Written consent to participate in the study• Male or female greater than or equal to 18 years of age• Symptoms consistent with greater trochanteric bursitis for greater than or equal to 3 months prior to screening (patient reported is acceptable)• Pain in hip for greater than 15 days over the last month (as reported by the patient).• Hip bursitis as determined by clinical examination and clinical features. Where Magnetic Resonance Imaging (MRI) data is available, it will be used to confirm the bursitis diagnosis. Also, pain relief in subjects that have been treated with bursal injections containing an anesthetic (such as ropivacaine) is in itself indicative of bursitis.• Body mass index (BMI) less than or equal to 40kg/m²• Ambulatory and in good general health• Willing and able to comply with the study procedures and visit schedules and able to follow verbal and written instructions.• Willing to abstain from use of protocol-restricted medications during the study 
Exclusion Criteria:
 
• Hip Arthroplasty• Hip osteoarthritis, iliopsoas bursitis, reactive arthritis, rheumatoid arthritis, psoriatic arthritis, ankylosing spondylitis, or arthritis associated with inflammatory bowel disease• History of local infection around the bursa.• Lack of pain relief with the intrabursal treatments containing an anesthetic• Intra-bursal treatment of any bursa with any of the following agents within three (3) months of screening: any corticosteroid preparation (investigational or marketed, including FX006); and/or six (6) months for any biologic agent (e.g., platelet rich plasma (PRP) injection, stem cells, prolotherapy, amniotic fluid injection; investigational or marketed).• Parenteral or oral corticosteroids (investigational or marketed) within 3 months of Screening• Inhaled, intranasal or topical corticosteroids (investigational or marketed) within 2 weeks of screening.• Females who are pregnant or nursing or plan to become pregnant during the study; women who plan to conceive
-----------------------------------	--

TEST PRODUCT, DOSE, AND ROUTE OF ADMINISTRATION	24 patients will be injected with the 5ml of FX006. This injection may be followed with up to 3ml of ropivacaine (depending on the capacity of the bursa), under ultrasound guidance.
CONTROL PRODUCT, DOSE AND ROUTE OF ADMINISTRATION	N/A
DURATION OF SUBJECT PARTICIPATION AND DURATION OF STUDY	The study will be completed in week 12 and all recorded patients' NPRS, PGIC and emergent findings, if any will be compiled into a HIPAA compliant database.
CONCOMITANT MEDICATIONS	
Allowed. Exclusions are listed below.
 
Prohibited:
 
 • Intra-bursal treatment of any bursa with any of the following agents within six (6) months of Screening: any corticosteroid preparation (investigational or marketed, including FX006), any biologic agent (e.g., platelet rich plasma (PRP) injection, stem cells, prolotherapy, amniotic fluid injection; investigational or marketed). • Parenteral or oral corticosteroids (investigational or marketed) within 3 months of Screening • Inhaled, intranasal or topical corticosteroids (investigational or marketed) within 2 weeks of Screening.
EFFICACY EVALUATIONS	Follow up telephone interviews will be performed in 1, 2, 4, 8, and 12 weeks to assess the patient for any adverse events and also to obtain the NPRS and PGIC scores.
SAFETY EVALUATIONS	Subjects will be questioned about any change in their perception of well-being or adverse effects if any, as compared to baseline

STATISTICS Primary Analysis Plan	
We plan to enroll 24 patients for the pilot study. This sample size is determined by the projected availability of eligible patients within the proposed study period (6 months).
 
Descriptive statistics will be reported for demographics and all clinical variables collected in this study.
 
For the efficacy evaluated by NPRS and PGIC, we will use appropriate summary statistics (e.g. mean + standard deviation for variables with normal distribution or median and interquartile range for variables with skewed distribution) to report NPRS and PGIC at each time point and analyze their changes over time.
 
For safety evaluated, we will report the frequency and percentage of patients who have received any treatment to emergent adverse events within 12 weeks.

---	---

1 BACKGROUND/RATIONALE

Zilretta is approved for intra-articular injection into the knee joint for treatment of osteoarthritis (1). There are ongoing studies for intra-articular injection into the other large joints including the shoulder and hip joints (2). To our knowledge there has been no prior study to prove efficacy of injection of the extended release steroid into the bursa. The bursae surrounding the hip joint including the iliopsoas and the greater trochanteric bursa are some of the larger bursae in the body. Conventional treatment for inflammation of these bursae is injection of corticosteroids (3). We believe that a long acting corticosteroid, if efficacious, can have a great impact. There is a significant population of patients suffering from chronic bursal pain, who might benefit. At our institution, bursal injection of the steroid in the region of hips is one of the most common locations, second only to joint injections. To our understanding, the bursa surrounding the hip are deep enough to avoid side effects associated with subcutaneous injection of steroid. The current proposal is a pilot study.

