2 STUDY OBJECTIVES

2.1 Primary Objective

The primary objective will be to determine the safety and efficacy of this drug in bursal injections by monitoring the improvement in the pain from baseline, as established using the using a Numeric Pain Rating Scale (NPRS) score at the end of 12 weeks. Safety of the extended-release 32 mg FX006 administered to patients with greater trochanteric bursitis will be evaluated with a follow-up to determine if there were any adverse events within 12 weeks from the time of injection.

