3. STUDY DESIGN

3.1 Study Overview

This is a consented, pilot study in patients with pain and bursitis involving the greater trochanteric bursa, with administration of 32 mg FX006. The study will be conducted in male and female patients 18 years of age or older with symptomatic greater trochanteric bursitis. Each patient will be screened for eligibility with an ultrasound to confirm the diagnosis of bursitis, in the absence of prior MRI imaging done in the preceding three months. Based on the inclusion/exclusion requirements, they will be offered participation in the study to receive an intra-bursal injection of 32 mg FX006. Eligible and participating patients will receive treatment under ultrasound image guidance to the greater trochanteric bursa. Patients will be followed up by phone at 1, 2, 4, 8, and 12 weeks and mean NPRS pain scores and PGIC scores will be recorded. Adverse events, if any, will be reported immediately to the primary physician and any subsequent follow-up will be reported. The study will be completed in week 12 and all recorded patients' NPRS, PGIC and emergent findings, if any will be compiled into a HIPAA compliant database.

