7.1 Treatment Plan

The patient will make a one-time visit to the outpatient radiology department at Memorial Hermann Hospital at the Texas Medical Center, and will be expected to stay for a maximum of 2 hours. Each patient will be consented for the procedure and a baseline assessment using the NPRS and PGIC measures will be made.

24 patients will be injected with the 5ml of FX006. This injection may be followed with up to 3ml of ropivacaine (depending on the capacity of the bursa), under ultrasound guidance. The data collected from the patient and subsequent follow-up will be maintained by the clinical team throughout the 12 weeks of the subject participation.

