8.1.4 Physical Examination

A focused physical examination will be performed by either the investigator or a sub-investigator who is a physician at screening.

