9 ADVERSE EXPERIENCE REPORTING AND DOCUMENTATION

9.1 Collection

Adverse events will be collected from the time of medication administration until completion of the follow-up telephone calls at week 12 or until subject participation in study ends.

The Investigator or other medical trained personnel will probe, via discussion with the subject, for the occurrence of Adverse Events during each subject contact and record the information in the source documents. Adverse events will be recorded in the patient CRF. Adverse events will be described by duration (start and stop dates and times), outcome, and treatment. The Investigator, or other medical trained personnel will also assess the seriousness and severity of the event, and relationship of the event to study drug according to the definitions below. If unrelated to study drug, the more likely cause of the event will also be assessed and recorded.

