16 APPENDIX 1: SCHEDULE OF STUDY ASSESSMENTS

	VISIT 1 (Day 1)	VISIT 2 (Week 2)	VISIT 3 (Week 4)	VISIT 4 (Week 8)	VISIT 5 (Week 12)
Informed Consent	X				
Medical History	X				
Abbreviated Physical Exam	X				
Height	X				
Weight	X				
Vital Signs	X				
Pregnancy Test (Urine)	X				
Dispensing or Administration of Study Drug	X				
Initiate Subject Diary	X				
Subject Diary Review		X	X	X	X
Concomitant Medication Review	X	X	X	X	X
Adverse Events	X	X	X	X	X

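### No injection-site item is prespecified, so the assumption that bursal depth avoids subcutaneous steroid effects is not specifically tested

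*Combined protocol and SAP*

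**What the plan says.** The rationale (Section 1, repeated in the Synopsis) says that "the bursa surrounding the hip are deep enough to avoid side effects associated with subcutaneous injection of steroid". It is hedged as the authors' understanding and carries no citation or depth figure. No other argument for local safety in the bursa is given.

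Section 2.1 makes safety part of the primary objective, to be evaluated by "follow-up to determine if there were any adverse events within 12 weeks from the time of injection". The arrangements for finding such events are these:

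- **Attendance.** Section 7.1: "The patient will make a one-time visit to the outpatient radiology department".
- **Examination.** Section 8.1.4: "A focused physical examination will be performed by either the investigator or a sub-investigator who is a physician at screening". Appendix 1 marks the physical examination on Day 1 only.
- **Follow-up.** Section 3.1: "Patients will be followed up by phone at 1, 2, 4, 8, and 12 weeks".
- **Question put to patients.** Synopsis, Safety Evaluations: "Subjects will be questioned about any change in their perception of well-being or adverse effects if any, as compared to baseline".
- **Collection by staff.** Section 9.1: the investigator or other trained personnel "will probe, via discussion with the subject, for the occurrence of Adverse Events during each subject contact".
- **Diary.** Appendix 1 starts a subject diary on Day 1 and lists "Subject Diary Review" at weeks 2, 4, 8 and 12, in columns labelled as visits. No section says what the diary records.

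Section 8.1.7 lists the attributes to record once an event is known (dates, severity, outcome, treatment, relatedness). It does not list events to ask about. Section 12 plans the frequency and percentage of patients with adverse events over 12 weeks, with no separate summary of local events.

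**The concern.** The rationale sets aside one class of local harm on grounds of anatomy, and no step in the data collection looks for that class. Painless colour change, thinning or dimpling at the side of the hip may not come up when a patient is asked by telephone about well-being or adverse effects in general. The patient may not have looked, or may not regard the change as an adverse effect.

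What is at stake is how a low count can be read. Section 12 expects the pilot to help establish safety and to inform a future trial. If few or no local events are recorded, the reader cannot tell whether they were rare or were not asked about. With 24 patients, one missed case moves the observed percentage by 1/24 = 4.2 points.

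**Working it through.** **1. Is there any step that targets local effects?** The arrangements above, set against what would be needed:

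| Possible source | In the plan? | Targets skin or subcutaneous change? |
|---|---|---|
| Examination after injection | None scheduled | No |
| Patient question (Synopsis) | Yes, general | No item named |
| Staff probing (9.1) | Yes, at each contact | Content not specified |
| Diary (Appendix 1) | Yes | Unknown; content undefined |
| Recorded injection depth | None | No |
| Separate local-event summary (12) | None | No |

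A change that the patient notices and mentions would be captured as an adverse event. A change that the patient does not notice or mention has no specified route into the data, unless the diary turns out to ask for it.

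**2. Is there a baseline for the site?** The Synopsis asks for change relative to baseline, but no site status is recorded before injection. Inclusion criterion 5 (Section 5.2) contemplates patients who have had earlier bursal injections. Exclusion criterion 4 (Section 5.3) bars intra-bursal corticosteroid only within three months and biologics within six. Section 6.2 gives six months for both; the two sections need reconciling, but earlier injections are possible under either. Old skin or fat changes could therefore be present on Day 1.

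**3. Scale of the effect on interpretation.** The plan has no figure to reproduce: 24 is set by patient availability, and no event rate or detection rate is given. The only document input is n = 24 (Section 12). The detection share s and the true rate p are assumptions.

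The exact (Clopper-Pearson) two-sided 95% upper limit for 0 of 24 is

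1 − 0.025^(1/24) = 0.142, or 14.2%.

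This bounds the rate of *recorded* events. If each event is recorded with probability s, independently, the number of patients with a recorded event is binomial with n = 24 and probability p·s. The limit on the true rate is then 0.1425/s, and the chance of recording none is (1 − p·s)^24.

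| Assumed s | Upper limit on true rate, 0 of 24 recorded | Chance of recording none, p = 10% | Chance of recording none, p = 5% |
|---|---|---|---|
| 1.00 | 14.2% | 8.0% | 29.2% |
| 0.75 | 19.0% | 15.4% | 40.0% |
| 0.50 | 28.5% | 29.2% | 54.5% |
| 0.25 | 57.0% | 54.5% | 73.9% |

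So a zero count has a limited but definite meaning under full detection, and its meaning weakens quickly as s falls. The table does not show what s is in this trial.

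**The case against.** The strongest reply is that this is a 24-patient, open-label, descriptive pilot whose safety aim is any adverse event within 12 weeks, and that general questioning fits that aim. Staff actively probe at five planned telephone contacts, and a diary is scheduled as well. The sentence about depth is a hedged background remark, not a hypothesis that the study sets out to test.

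Much of this stands, and it rules out several stronger readings that a reader might infer:

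- *That nobody asks about adverse events, or that reporting is wholly unsolicited.* Section 9.1 says otherwise. What is missing is a fixed list of items.
- *That an open telephone question is the only ascertainment after Day 1.* Appendix 1 schedules a diary. Since its content is undefined, it can be neither credited with covering local effects nor said to omit them.
- *That depth is the protocol's main safety assumption.* The documents do not rank it. It is the only local-safety argument they state.
- *That the plan will present the absence of local effects as a finding.* Section 12 plans only the frequency and percentage of patients with adverse events.
- *That the local event rate is biased downward by a known amount.* The documents give no true rate and no detection rate.

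What the reply does not remove is that probing without prescribed content may differ between callers, and that no item directs anyone to the injection site. The small sample is no answer either: with few patients, each event carries more weight.

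**Conclusion.** The point holds as a gap in data collection. The plan states an uncited assumption about local safety, includes safety in the primary objective, and prespecifies no local skin or subcutaneous item, no examination after Day 1 and no site baseline. Painless changes may be under-recorded, and the assumption is not specifically tested. It is not wholly untested, because a change that is noticed and reported would be recorded.

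The size of any under-recording cannot be determined from the documents. The one firm number is conditional: 0 of 24 gives an exact upper limit of 14.2% on the true rate only if every event is detected. The higher limits (19.0% to 57.0%) rest on assumed detection shares of 75% to 25%, the same and independent across patients. The change is worth making because it is cheap and must be in place before the first injection; an early change that later resolves may not be recoverable.

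**What to change.** In Sections 8.1.7 and 9.1 and in Appendix 1:

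- Add a short fixed yes/no injection-site checklist: colour change, thinning or dimpling, and lump; optionally redness, warmth and drainage.
- Record it on Day 1 before injection as a baseline, and again at each planned call. Section 9.1 starts adverse event collection at administration, so the Day 1 entry should be a baseline record and not an adverse event.
- At each call, ask the patient to look at the site before answering, and record an onset date for any positive item.

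In Section 12, report new or worsened items as n/N with exact 95% confidence intervals, separately from spontaneously reported adverse events. State that detection is by self-report, so the intervals still do not assume complete detection.

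Define what the subject diary records. Reconcile Appendix 1 with Sections 3.1 and 7.1: its later columns are labelled Visit 2 to Visit 5 where the text describes one attendance and telephone follow-up, and it has no column for the week 1 call.

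The cost is one case report form page and a minute or two per contact, with no added visit or examination. The downside is a higher count of minor events, which the separate reporting keeps visible.

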2 STUDY OBJECTIVES

2.1 Primary Objective

The primary objective will be to determine the safety and efficacy of this drug in bursal injections by monitoring the improvement in the pain from baseline, as established using the using a Numeric Pain Rating Scale (NPRS) score at the end of 12 weeks. Safety of the extended-release 32 mg FX006 administered to patients with greater trochanteric bursitis will be evaluated with a follow-up to determine if there were any adverse events within 12 weeks from the time of injection.

2.2 Secondary Objectives

Secondary objective is to determine any alteration in the Patient Global Impression of Change (PGIC) measure. This is used as an indicator to assess the patient's impression to change in treatments to chronic pain.

3. STUDY DESIGN

3.1 Study Overview

This is a consented, pilot study in patients with pain and bursitis involving the greater trochanteric bursa, with administration of 32 mg FX006. The study will be conducted in male and female patients 18 years of age or older with symptomatic greater trochanteric bursitis. Each patient will be screened for eligibility with an ultrasound to confirm the diagnosis of bursitis, in the absence of prior MRI imaging done in the preceding three months. Based on the inclusion/exclusion requirements, they will be offered participation in the study to receive an intra-bursal injection of 32 mg FX006. Eligible and participating patients will receive treatment under ultrasound image guidance to the greater trochanteric bursa. Patients will be followed up by phone at 1, 2, 4, 8, and 12 weeks and mean NPRS pain scores and PGIC scores will be recorded. Adverse events, if any, will be reported immediately to the primary physician and any subsequent follow-up will be reported. The study will be completed in week 12 and all recorded patients' NPRS, PGIC and emergent findings, if any will be compiled into a HIPAA compliant database.

4 CRITERIA FOR EVALUATION

4.1 Primary Endpoint

The primary endpoint will be the improvement in the pain from baseline, at the end of week 12 as determined by the NPRS pain score.

4.2 Secondary/Exploratory Endpoints

The secondary endpoint will be any alteration in the PGIC measure, at the end of week 12.

4.3 Safety Evaluations

Incidence of adverse events will be recorded and reported to appropriate bodies including the UTHealth IRB and FDA, if indicated.

5 SUBJECT SELECTION

5.1 Study Population

Subjects with a diagnosis of bursitis of greater trochanter, who meet the inclusion and exclusion criteria will be eligible for participation in this study.

5.2 Inclusion Criteria

1. Written consent to participate in the study
2. Male or female greater than or equal to 18 years of age
3. Symptoms consistent with bursitis of greater trochanter for greater than or equal to 3 months prior to Screening (patient reported is acceptable)
4. Pain in hip for greater than 15 days over the last month (as reported by the patient)
5. Hip bursitis as determined by clinical examination and clinical features. Where Magnetic Resonance Imaging (MRI) data is available, it will be used to confirm the bursitis diagnosis. Also, pain relief in subjects that have been treated with bursal injections containing an

anesthetic (such as ropivacaine) is in itself indicative of bursitis

6. Body mass index (BMI) less than or equal to 40 kg/m²
7. Ambulatory and in good general health
8. Willing and able to comply with the study procedures and visit schedules and able to follow verbal and written instructions.
9. Willing to abstain from use of protocol-restricted medications during the study

